The study is posted on the Clinical Center www protocol site, which explains the characteristics of the patients sought and the main purposes of the study. A phone number is listed, where inquirers can obtain more information and enter a mailing list for receiving information packets, including consent forms. Any other advertisement will be submitted to the IRB for approval.

NIH employees may participate in this protocol. Patients do not receive payments or compensation. Travel costs may be provided after the initial visit, or including the initial visit if there is financial need.

Benefits, Risks, and Hazards

Benefits

Patients benefit from initial and follow-up general and endocrinologic evaluations, including imaging studies. Patients in whom a tumor causing ectopic Cushing syndrome is found are offered surgery at the NIH. Those with Cushing's disease may undergo surgery at the NIH. Patients with hypercortisolemia due to occult tumor will be offered medical treatment (i.e. administration of drugs blocking cortisol synthesis or cortisol action) or bilateral adrenalectomy.

Since there is a possibility that patients may benefit from detection of previously unrecognized tumor, information gained from this study may affect future clinical management of patients with ectopic Cushing syndrome.

This is an elective study. Thus, nonparticipation does not affect a patient's clinical care, but patients electing not to participate in the research component will be returned to the care of their outside physicians.

Risks and Hazards

1. *Risks related to radiation* from the administration of radioactive drugs and attenuation CT scans. The annual total effective research radiation dose to patients receiving both FDOPA PET/CT and L-OCT after mifepristone, is 3.12 rem. It will be correspondingly less for those who receive only one of these research studies. (Please also see Concern About Radiation" above re: radiation from other studies). To minimize bladder exposure, FDOPA patients will be asked to void after approximately 30 min., and every 90 minutes for the 6 hours following completion of the PET scan. Patients will be asked to void every 2 – 4 hours for 12 hours after the Octreoscans.

2. *Vein cannulation* can cause pain, bleeding, thrombosis, or infection. Bleeding is prevented by local pressure applied for 5-10 minutes after catheter removal. Infection is prevented by use of clean technique and the relatively short time the catheter is in place. Fainting can occur during insertion of a vascular catheter in subjects who are sitting; however, in this study, the subjects are supine. An indwelling line will be placed to reduce the number of needle sticks needed for phlebotomy purposes.

3. *Vein cannulation for IPSS* may cause femoral hematoma, arteriovenous fistula, bruising or discomfort or transient arm anesthesia. Femoral vein puncture is sometimes more difficult in patients with Cushing syndrome because of marked obesity. There is a slight, but definite risk of entering the femoral artery that might result in bleeding, a groin hematoma or arteriovenous fistula. However, we currently have available a "smart" needle with an ultrasound transducer incorporated in the tip which enables us to puncture veins even in the most difficult subjects so that we anticipate < 1% rate of these complications. Patients experience mild discomfort and may have visible bruising in the groins after the procedure. Cannulation of the internal jugular vein led to transient loss of sensation in the arm in one patient at the NIH, presumably because of infiltration of the cervical nerves by the anesthetic.

4. *CRH administration* has minimal risk. Up to 20% of patients experience flushing and a smaller percentage experience a metallic taste. CRH has been given safely on multiple occasions to the same patients, as proposed here, in the context of CRH stimulation test or dexamethasone test. CRH has been given more than 1000 times at the NIH and many thousands of times world-wide. The commercially available formulation is used (Ferring Corp.).

5. *Contrast allergy* to radiographic dye. There is a very small (< 0.5 %) risk of new contrast allergy. Patients with a known dye allergy will receive prophylactic treatment.

6. *Anemia*. The maximum total amount of blood drawn for the standard medical tests is about 265 ml. The study is not to be performed if the patient's previous and predicted total blood withdrawal for the six weeks prior to the study is more than 450 ml.

7. *The use of Foley or condom catheters*, if needed, may be associated with some local discomfort and an increased risk of urinary tract infection.

8. *Possible emotional responses during scans*. A patient can develop nervousness, anxiety, and panic attacks during any scanning procedure. In such a case, the study is discontinued and the patient evaluated and treated if necessary.

9. *MRI evaluations may cause claustrophobia*. Should this occur the study will be stopped and re-scheduled with administration of a sedative.

10. *Risk of adrenal insufficiency due to mifepristone*. Subjects without Cushing syndrome who received long-term mifepristone administration showed antiglucocorticoid effects at a daily dose of 10 mg/kg, which is about 5 – 10 fold greater than that required to demonstrate antiprogestin effects (41). Overtreatment with mifepristone may lead to adrenal insufficiency. In case of suspicion of adrenal insufficiency (defined as hypotension and the presence of severe symptoms of nausea, vomiting or diarrhea), we will stop mifepristone and initiate glucocorticoid substitution with hydrocortisone or dexamethasone. Therapy will take into account results from pharmacology studies demonstrating that 1 mg dexamethasone or 30 mg hydrocortisone antagonizes 400 mg mifepristone. These individuals will not receive the second L-OCT.

Patients with isolated symptoms (nausea, vomiting, diarrhea, weight loss, anorexia or isolated fatigue) will be monitored closely as an inpatient in the Clinical Center. Except for diarrhea, these symptoms are expected possible effects of the study treatment and are not systematically indicative of adrenal insufficiency. No modification of treatment will be initiated unless symptoms worsen or patient develops new symptoms. Hyponatremia and/or hyperkalemia can be indicative of adrenal insufficiency but also can be explained by other causes and will require further investigation.

Less specific adverse events as maculopapular rash also have been observed.

11. *Risks associated with use of gadolinium-based contrast agents(GBCAs) for magnetic resonance imaging(MRI)*. The FDA has issued a warning that certain groups of patients are at risk for nephrogenic

systemic fibrosis after receiving gadolinium. In order to reduce unnecessary risks, serum creatinine and GFR will be obtained prior to any gadolinium-based procedure. Gadolinium will be withheld in patients with acute or chronic renal insufficiency (GFR<60ml/min), unless deemed necessary in order to verify CT scan findings required for clinical management decisions. The vast majority of patients receiving gadolinium-based contrast agents have no symptoms related to the injection of this medication. Mild symptoms that may occur include coldness in the arm at the time of injection, a metallic taste, headache, and nausea. In an extremely small number of patients, more severe symptoms have been reported including shortness of breath, wheezing, hives, and lowering of blood pressure

Consent Process and Documents

When patients or physicians contact the research team to indicate an interest in participating in the study, a consent form will be provided and any questions will be answered. The study will be explained verbally and all questions and concerns addressed at the first NIH visit, at which time written informed consent will be obtained. Members of the research team authorized to obtain consent are [name] and [name]. A record of communication of this information and of the consent to participate in the study is placed in the medical record and the patient receives a copy of the document. The research team retains a copy. The right of the subjects to withdraw from this study or to refuse any procedure is made clear.

Three consent forms will be used to reflect the various options available to current patients (based on number of previous scans) and for new patients. All returning patients will be consented again with the appropriate consent. These will include:

1. Consent for previous patients who have had their maximum of two F-DOPA PET examinations and three H-OCT examinations. On each admission they will get only standard clinical imaging (CT, MRI, 6 mCi OCT).
2. Consent for (previous or new) patients who are hypercortisolemic. On each admission they will get standard clinical imaging (CT, MRI, 6 mCi L-OCT) as well as F-DOPA PET/CT and one octreoscans with mifepristone. Because most patients are hypercortisolemic at only one visit, we anticipate that they would need a separate subsequent consent, unless they have recurrent disease.
3. Consent for (previous or new) patients who are hypercortisolemic and refuse or are not candidates for mifepristone, or those who are not hypercortisolemic. On each admission they will get standard imaging (CT, MRI, 6 mCi OCT) as well as F-DOPA PET and high dose octreoscan (if low dose is negative), up to the maximum number of PET and high dose octreoscans.

We do not plan or anticipate the enrollment of non-English speaking subjects; however they are not excluded from participation either. Should a non-English speaking subject be eligible for enrollment, IRB approval will be obtained for use of the short form consent process in the absence of a fully translated consent document as outlined in SOP 12.9.1, under the provisions of 45 CFR 46.117(b)(2). IRB approval will be obtained according to IRB guidance prior to obtaining informed consent from the potential study participant/s.

Employee enrollment is not anticipated in this protocol, but if an employee wants to be enrolled in the study with the prospect of direct benefit in accordance with the policy SOP 14F.3.1 the PI is not required to amend the protocol. However the PI will take the following steps to ensure that there are adequate protections in place to protect the confidentiality of employee health information and minimize any pressure or discomfort of the employee with consent process.

1. The PI or responsible AI will make the NIH Information Sheet on Employee Research Participation available to employees who are considering enrolling in research to help them understand the possible consequences. Also, the PI or AI will make a copy of the NIH policy 2300-630-3 available to employee.
2. If PI or AI is the supervisor of the employee-subject an independent person (i.e. bioethics staff) will monitor consent process.
3. The PI will require that study staff who may have contact with sensitive data about a co-worker or subordinate complete the Just-in-Time CITI course "Biomedical –Vulnerable Subjects-Workers/Employees".

Confidentiality and use of retained tissue specimens

Confidentiality of patients is assured according to the laws of the State of Maryland. When results of a study such as this are reported at meetings or in medical journals, the identification of those patients taking part is withheld. Medical records of Clinical Center patients are maintained according to current local requirements and are made available for review, as required by the FDA or other authorized users.

legal requirements and are made available for review, as required by the FDA or other authorized users, only under the guidelines established by the Federal Privacy Act. All data are kept in locked files.

Patients will be asked to consent to the future use of urine, blood and tumor samples. If they consent to such use, samples may be used in the future, with identifiers, for studies not described here, without obtaining new informed consent. Only studies related to Cushing's syndrome or the biology of tumors would be undertaken. Investigators who are not part of this protocol may procure tumor tissue in the operating room only with authorization from [name]. Tissue samples may be shared with collaborators, without personal identifiers. All samples will be coded without personal identifiers and will be stored in accordance with NIH and NICHD biospecimen policies.

Other Interested Parties and Collaborators

The NIH has a Cooperative Research And Development Agreement (CRADA) with Laboratoire HRA-Pharma, in Paris, France. The intention of the CRADA is to develop mifepristone for the treatment of Cushing's syndrome, for use as an adjunctive agent for Octreoscan, and for use as a diagnostic agent.

REFERENCES

2. Jex RK, van Heerden JA, Carpenter PC, Grant GS. Ectopic ACTH syndrome. Diagnostic and therapeutic aspects. *Am J Surg* 1985; 149:276-282.
5. Orth DN. Cushing's syndrome. *New Engl J Med* 1995; 332:791-803.
6. Orth DN. Corticotropin-releasing hormone in humans. *Endocr Rev* 1992; 13:164-191.

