Between 10% and 20% of patients with hypercortisolism (Cushing syndrome) have ectopic production of adrenocorticotropin hormone (ACTH) that causes cortisol excess. In approximately 50% of these patients, the source of ACTH cannot be found despite very detailed and extensive examination including imaging studies such as computed tomography scanning, magnetic resonance imaging, and octreotide scan (Octreoscan) using the standard dose of indium- 111 pentetreotide ([¹¹¹In-DTPA-D-Phe]-pentetreotide). The sensitivity and specificity of these imaging studies depends on anatomic alterations and/or the dose and adequate uptake of radiopharmaceutical. In contrast, positron emission tomography (PET) has the ability to detect pathologic tissue based on physiologic and biochemical processes within the abnormal tissue. This protocol tests whether [¹⁸F]-L-3,4-dihydroxyphenylalanine (¹⁸F-DOPA) can be used to localize successfully the source of ectopic ACTH production. In addition the study examines whether administration of the glucocorticoid antagonist mifepristone can improve the sensitivity of the standard dose Octreoscan. Eligible patients participating in this arm of the study will have a second standard dose

scan. Others will receive a higher dose octreoscan instead.

INTRODUCTION

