However, H-OCT delivers a substantial radiation dose, particularly when coupled with the L-OCT as is done here. In particular, the bladder receives high dose because these radiopharmaceuticals are excreted by the kidneys. (See later: concern about radiation). Thus, while the benefit-to-risk ratio has been considered acceptable because of improved localization and the high morbidity and mortality experienced by patients with this disease, a lower radiation dose would be preferable. To this end, we propose evaluation of whether the antiglucocorticoid mifepristone can improve L-OCT sensitivity in patients with active hypercortisolism. ¹¹¹In-DTPA-D-Phe]-pentetreotide binds primarily to the somatostatin receptors subtypes (sst) 2 and 5. There is a large variability in functional sst2 receptor expression in these tumors (18), which may account for failure of OCT detection of tumors. One explanation for this variability is that glucocorticoids can directly down-regulate the expression of sst2 in neuroendocrine cells *in vitro* (19-20). If this is the case *in vivo*, antagonism of glucocorticoid action would be expected to relieve this down-regulation, and possibly allow for conversion of a negative OCT to a positive study. Two patients treated with mifepristone at the NIH and in the Netherlands, who converted from a negative to a positive scan, generated this hypothesis (22). However, the interval between the scans was from 2 – 12 months. To test this hypothesis formally, we will administer mifepristone to individuals whose initial L-OCT is negative, and will obtain a second L-OCT after ten days of mifepristone 600 mg daily. This dose is expected to antagonize most glucocorticoid effect in patients with ectopic ACTH secretion.

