(c) Can the administration of mifepristone, 600 mg daily for 10 days, convert a negative standard 6 mCi OCT (L-OCT) to a subsequent positive result?

MRI

(d) Does gated chest MRI detect more lesions than routine MRI?

STUDY DESIGN AND METHODS

Standard Medical Evaluation of Cushing Syndrome

We will evaluate patients at the Clinical Center on an inpatient ward. Each subject will undergo a complete medical history, physical examination, and chemical screening tests, including acute care panel, liver function tests, thyroid function tests, complete blood count, plasma ACTH levels (30 ml of blood), and urine free cortisol. Patients also undergo measurement of diurnal cortisol in blood and saliva to confirm the diagnosis of Cushing syndrome (20 ml of blood). This is followed by a CRH stimulation test (30 ml of blood), inferior petrosal sinus sampling (IPSS; 90 ml of blood) and 8 mg overnight dexamethasone suppression test (10 ml of blood). Patients undergo MRI before IPSS: those with a mass greater than 6 mm diameter may not need IPSS, if CRH and dexamethasone suppression tests are compatible with Cushing's disease. All of these tests are performed as part of the standard evaluation of Cushing syndrome.

The initial diagnostic evaluation lasts up to 14 days. Where not limited by medical or social concerns, and where guesthouse accommodation is available, it may be performed in the outpatient/day hospital areas except for overnight stays associated with diurnal sampling. Patients whose results are consistent with Cushing's disease will be referred for transsphenoidal surgery, and will not undergo the imaging studies described below.

Patients whose evaluation indicates ectopic ACTH secretion (generally, lack of response to CRH, dexamethasone and lack of central to peripheral ACTH gradient on IPSS) will undergo standard, medically-indicated, imaging studies for localization of the tumor, including CT (neck, chest, abdomen, and pelvis), 1.5 T MRI (neck, chest, abdomen, and pelvis), and 6 mCi standard Octreoscan (L-OCT). Women will undergo a serum pregnancy test within 24 hrs before administration of any isotope.

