Patients without active hypercortisolism in whom the standard Octreoscan is negative (or those ineligible for the mifepristone study) will undergo H-OCT. Because of interference we will wait at least one week after dosing a low dose Octreoscan before doing a H-OCT. The IRB previously agreed that this would be a medically indicated procedure in these patients. However, because it adds significantly to the cumulative radiation exposure, we have decided to limit this to three scans at intervals of at least one year.

The duration of standard imaging studies is about 10-15 minutes for either CT of the neck, chest, abdomen, or pelvis and 1-2 hours for either MRI of the pituitary, chest, abdomen, or pelvis, and 1-3 hours for Octreoscan (see below).

Research Procedures

Eligible patients with active hypercortisolism will receive the mifepristone-L-OCT combination as a research study (see below). Patients will undergo F-DOPA PET/CT as a research study, up to two studies with an interval of at least 12 months. Patients may undergo imaging before or after treatment of ectopic Cushing syndrome (if they have evidence of active ectopic ACTH secretion). Because of interference and to allow for administration of mifepristone, we will wait at least ten days after dosing a low dose Octreoscan before doing a second L-OCT. A gated chest MRI will be obtained using a 3 Tesla magnet with T1 and T2 sequences. Blood will be collected into one heparin and serum tube and an aliquot of urine will be retained for additional clinical or future research studies related to hypercortisolism. As an example, we previously studied the utility of pro-calcitonin using research samples collected under another protocol (39). Patients will be asked to consent to the future use of tumor samples. If they consent to such use, samples may be used in the future, with identifiers, for studies not described here, without obtaining new informed consent. Only studies related to Cushing's syndrome or the biology of tumors would be undertaken.

F-DOPA PET/CT procedures

The research team is responsible for ensuring that PET-specific regulations and procedures are followed.

Patients are studied in the PET Department scanning facility at the Clinical Center after a minimum of 6 hours fasting. A plastic catheter is inserted into an arm vein. Patients receive carbidopa, 200 mg, orally 60 minutes before the scheduled injection of F-DOPA.

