(a) *Compared to other imaging techniques, is the sensitivity and specificity of F-DOPA PET/CT higher in detecting the source of ectopic ACTH production in patients with known and unknown tumor localization?* To determine this, we will calculate the sensitivity, specificity, positive and negative values in patients with proven tumors and compare these with the results from the other modalities. Confidence intervals will be calculated and overlapping results will indicate that the modalities are similar. We cannot perform these calculations for unknown tumors, but can compare the overall percentage of tumors found of all imaged using each technique.

(b) *Does a correlation exist between F-DOPA uptake and the type of tumor, its size and proliferative activity?* To do this, we will evaluate the percent of each type of tumor that has a positive F-DOPA scan. Confidence intervals will be used to compare across tumor types. Univariate logistic regression will be performed using size and mitotic index as the variables.

(c) *Can the administration of mifepristone, 600 mg daily for 10 days, convert a negative standard 6 mCi OCT (L-OCT) to a subsequent positive result?* This will be a descriptive analysis, indicating the percentage of tumors that convert the test to a positive result. A post-hoc analysis will compare this percentage to the historical percentage of tumors that are positive on high but not low dose octreoscan.

(d) *Does gated chest MRI detect more lesions than routine MRI?* A similar approach will be used, to look at the percentage of known tumors that are detected by gated vs routine MRI and comparing confidence intervals around those values.

PHARMACEUTICAL AND RADIATION SAFETY

Pharmaceutical Information: F-DOPA

F-DOPA is a radiolabeled amino acid (^{18}F has a 109 minute half-time). It is approved by the FDA for use under IND # 35513. [name], Chief, PET Department, holds the IND. F-DOPA is produced as outlined in the IND. F-DOPA has been used in many protocols at the NIH and at other centers throughout the world. The formulation is prepared on the day of use and assayed in a dose calibrator. The total amount of F-DOPA will typically be ~2.4 mg and will not exceed 6.5 mg.

Pharmaceutical Information: [^{111}In -DTPA-D-Phe]-pentetreotide

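### The mifepristone aim is worded as better L-OCT sensitivity, but the planned data measure only conversion of negative scans, and the general sensitivity and McNemar analyses cannot validly cover it

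*Combined protocol and SAP*

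**What the plan says.** The mifepristone question appears in two forms.

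- **As sensitivity.** The opening summary states that "the study examines whether administration of the glucocorticoid antagonist mifepristone can improve the sensitivity of the standard dose Octreoscan". The Introduction proposes to evaluate "whether the antiglucocorticoid mifepristone can improve L-OCT sensitivity in patients with active hypercortisolism".
- **As conversion.** Later in the same paragraph the Introduction gives the re-scan rule: "we will administer mifepristone to individuals whose initial L-OCT is negative, and will obtain a second L-OCT". Objective (c) asks whether mifepristone can "convert a negative standard 6 mCi OCT (L-OCT) to a subsequent positive result". The analysis of (c) under Data Collection and Evaluation reads: "This will be a descriptive analysis, indicating the percentage of tumors that convert the test to a positive result". A post-hoc comparison with the historical high-dose (H-OCT) percentage follows.

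Two further parts of the plan bear on this.

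- Data Collection and Evaluation, before it reaches the individual objectives, plans accuracy measures, sensitivity among them, for every scan under study, and McNemar's test for paired data. It then presents the objective-specific methods as additions to McNemar's test for the four objectives. Objective (c) is not excepted.
- Research Procedures describes the re-scanned group without the negative-scan condition: "Eligible patients with active hypercortisolism will receive the mifepristone-L-OCT combination as a research study". The second consent form listed under Consent Process and Documents also omits it.

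The section justifying the number of subjects gives no sample size for the mifepristone question and says there were essentially no data to base one on.

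**The concern.** Sensitivity of an L-OCT on mifepristone and conversion among L-OCT negatives are different quantities. The first needs to know what happens to tumors that were already visible; the second ignores them. Under the Introduction's rule a visible tumor is never scanned on drug, so a positive scan turning negative cannot be recorded. The data then support a statement about the extra yield of a second scan after a negative first one. That yield cannot be negative, whatever the drug does.

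The mismatch could reach the results through the general analysis paragraph. If per-scan sensitivity and McNemar's test are applied to (c) as written, both are computed on patients selected for a negative first scan, and both can move in one direction only. A further limit is that no second L-OCT off drug is planned. Some negative scans may turn positive on repetition through ordinary variation in uptake, acquisition or reading, and the plan has no means of separating these from a drug effect.

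**Working it through.** **1. The plan's own figures.** The Introduction reports 59% L-OCT sensitivity in 27 proven tumors and H-OCT positivity in 7 of 12 L-OCT negatives.

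- 7/12 = 58.3%, which matches the stated 58%.
- 16/27 = 59.3%. The count of 16 is inferred; 15/27 = 55.6% and 17/27 = 63.0% do not round to 59%.
- 27 − 16 = 11 negatives, against an H-OCT denominator of 12, so the two figures may come from different patient sets.

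**2. What is and is not observed.** Let s be baseline sensitivity, c the conversion rate among L-OCT-negative tumors, and l the rate at which L-OCT-positive tumors would be negative on the second scan.

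- Sensitivity of the second scan alone: s(1 − l) + (1 − s)c
- Yield of the sequence (L-OCT, then a second L-OCT if negative): s + (1 − s)c

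The Introduction's rule observes c but never l. The sequence yield is at least s for every c ≥ 0. For illustration, take s = 16/27 and borrow c = 7/12 from H-OCT, since the protocol gives no rate for mifepristone. The sequence yield is 0.593 + 0.407 × 0.583 = 83.0%. The second scan alone would have sensitivity 83.0% at l = 0, 77.1% at l = 0.10, 71.2% at l = 0.20 and 59.3% (no change) at l = 0.40. The same observed c fits all of these.

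**3. McNemar's test applied to (c).** The exact test compares negative-to-positive with positive-to-negative changes. The second count is zero by design, so with k conversions the two-sided p is 2 × 0.5^k:

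- k = 5: 0.0625
- k = 6: 0.031

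Any six conversions are therefore significant at 5%, however many negatives were re-scanned.

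**4. Conversions with no change in sensitivity.** Suppose both scans have sensitivity s but disagree at random, with a fraction l of positives lost on repeat. Equal sensitivity requires (1 − s)c = s·l, so c = s·l/(1 − s) = 16l/11. The values of l are assumptions; the protocol gives no repeatability figure.

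| l (assumed) | c among negatives | Sequence yield, s + s·l |
|---|---|---|
| 5% | 7.3% | 62.2% |
| 10% | 14.5% | 65.2% |
| 20% | 29.1% | 71.1% |
| 30% | 43.6% | 77.0% |

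If positives were re-scanned too, the losses would offset these conversions in McNemar's test. Here they are not seen.

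**5. Steps 3 and 4 together.** With chance conversion of 29%, the binomial probability of at least six conversions is 0.103 among 12 negatives, 0.545 among 20 and 0.905 among 30. These numbers of negatives are also assumed. The literal McNemar analysis would often be significant with no drug effect.

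**The case against.** The strongest reply is that the governing text is consistent. The summary and Introduction give motivation and define no endpoint; objective (c) and its analysis agree with each other; and the analysis is labelled descriptive. The Introduction itself moves from sensitivity to conversion within one paragraph. It also describes the 7/12 H-OCT result in L-OCT negatives as additional sensitivity, so the protocol arguably uses the word to mean added yield. All of this stands, and it makes the point a mismatch between a stated aim and what is measured, not a numerical error. It does not answer the general analysis paragraph, which brings in per-scan sensitivity and McNemar's test without excepting (c).

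A second reply is that the negatives-only premise is not uniform, since Research Procedures and the second consent form omit the condition. That is correct. If those sections governed and positives were re-scanned, sensitivity could be estimated. But nothing in the analysis plan describes using re-scanned positives, so the inconsistency is a further reason to align the text.

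Three stronger readings are tempting and are not supported:

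- A reader might infer that the study will announce improved sensitivity, or recommend mifepristone before a single L-OCT. No section plans either; mifepristone is placed after a first L-OCT, as an alternative to H-OCT.
- A reader might infer that sensitivity on mifepristone could plausibly be as low as 24%, from (11/27) × (7/12) = 23.8%. That requires every visible tumor to disappear. It is a logical limit, and it runs against the mechanism that the Introduction proposes.
- A reader might infer that conversion is not worth measuring. Among proven tumors it is a legitimate measure of the added yield of a second scan.

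**Conclusion.** The point holds as a mismatch between the wording of the aim and what objective (c) measures, with a practical consequence through the general analysis paragraph. If only L-OCT-negative patients are re-scanned, the sensitivity of an L-OCT on mifepristone is not estimable, and McNemar's test and a per-scan sensitivity for (c) can only favour mifepristone; six conversions suffice for exact p = 0.031. These conclusions follow from the design and need no assumed rates. Separately, without an off-drug repeat scan, conversions cannot be credited to mifepristone alone. The size of that problem is illustrative: 29% of negatives converting with no change in sensitivity rests on an assumed 20% loss among positives and on a baseline of 16/27. That baseline is inferred from a series which the Introduction does not restrict to active hypercortisolism. The text should be corrected, but no collected data are invalidated.

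**What to change.** 1. In the summary and Introduction, state the aim as the added yield of a second L-OCT on mifepristone after a negative L-OCT.
2. In the analysis of (c), report the conversion percentage among L-OCT-negative patients with proven tumors, with an exact confidence interval. As a guide to the precision to expect, 7/12 has an exact 95% interval of 27.7% to 84.8%. If wanted, add the two-step yield, labelled as a sequence; it cannot fall below that of L-OCT alone and is not evidence of a drug effect.
3. In Data Collection and Evaluation, except (c) from the McNemar and per-scan sensitivity analyses. State that the sensitivity of a mifepristone L-OCT used alone is not estimated, and that the yield cannot be credited to mifepristone alone.
4. Reconcile Research Procedures and the second consent form with the Introduction on whether only L-OCT-negative patients are re-scanned. Items 1 to 3 assume that the Introduction's rule is the one analyzed; which rule applies is for the investigators to settle.

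The cost is rewording and one interval from data already planned. No scan, patient or radiation exposure is added. The downside is a narrower claim.
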